11 SAFETY EVALUATION

11.1 Definitions

11.1.1 Adverse event (AE)

An adverse event (AE) refers to any untoward medical occurrence in a clinical investigation subject and which does not necessarily have a causal relationship with the treatment. AEs include but are not limited to: Abnormal laboratory findings; clinically significant symptoms and signs; allergies;

According to the needs of management, safety monitoring (reporting of AEs or SAEs) should be performed from the signing of the informed consent form by the subject to 28 days after the last dose.

11.1.2 Adverse drug reaction (ADR)

All toxicities and unintentional reactions to a drug associated with any dose should be considered as adverse drug reactions (ADRs). A drug reaction means that a potential causal relationship between the drug and AE is at least reasonable, which means that the relationship cannot be excluded.

11.1.3 Serious adverse event (SAE)

An SAE refers to a medical occurrence during the clinical trial that results in hospitalization, prolonged hospitalization, disability, incapacity, life threatening events or death, or congenital malformation. The following unexpected medical events are included:

- Events resulting in death;
- Life-threatening events (defined as events where the subject is at immediate risk of death at the time of the onset);
- Events resulting in hospitalization or prolonged hospitalization;
- Events resulting in permanent or serious disability/incapacity;
- Congenital anomalies or birth defects.
- Overdose.
- Pregnancy during the clinical trial.

Criteria for other SAEs specified in the protocol:

- Cardiac insufficiency - defined as any symptom or sign of reduced LVEF (NCI CTCAE Grade 3), or LVEF reduced by $\geq 20\%$ from baseline and below the lower limit of normal (or reduced to $< 50\%$).

- ALT $> 5 \times$ ULN and total bilirubin $> 2 \times$ ULN (such as direct bilirubin $> 35\%$; the bilirubin ratio should be measured).

Note: If possible, the bilirubin ratio assay should be completed. If the test cannot be performed due to limited capacity and the subject has reached the criteria of total bilirubin of $> 2 \times$ ULN, the event should be reported as an SAE.

Progressive disease

Progressive disease (including progressive signs and symptoms) should not be reported as an SAE. However, death due to progressive disease during the trial or safety reporting period should be reported as an SAE. Hospitalizations due to signs and symptoms of progressive disease should not be reported as an SAE. During the trial or safety reporting period, if the final outcome of the cancer is death, then the event leading to death should be reported as an SAE.

Other anti-tumor treatments

If a subject is to start another anti-tumor treatment, AEs except death will be reported until the start of the new anti-tumor treatment. Death that occurs within the SAE reporting period after study treatment is completed should be reported regardless of whether the patient received other treatment.

Hospitalization

During the trial, AEs resulting in hospitalization or prolonged hospitalization should be considered serious AEs. Any initial hospital admission by a medical facility meets this criterion (even if less than 24 hours).

Hospitalization does not include the following:

- Hospitalization at a rehabilitation institution
- Hospitalization at a sanatorium
- General emergency admission
- Day surgery (e.g., outpatient/same-day/ambulatory surgery)

Hospitalization or prolonged hospitalization not related to the worsening of adverse events is not considered an SAE. For example:

- Hospitalization due to pre-existing disease without occurrence of new AEs or worsening of the pre-existing disease (e.g., for testing persistent laboratory abnormalities that started before the study);
- Hospitalization for management reasons (e.g., annual routine physical examination);

- Hospitalization during the study as specified in the study protocol (e.g., as required by the protocol);
- Elective hospitalization unrelated to the deterioration of an AE (e.g., elective cosmetic surgery);
- Scheduled treatment or surgery that should be documented in the entire study protocol and/or in subject's individual baseline information;
- Hospitalization merely for use of blood products.

Diagnostic or therapeutic invasive (e.g., surgery) or non-invasive procedures should not be reported as adverse events. However, the disease condition leading to such procedures should be reported if it meets the definition of an adverse event. For example, acute appendicitis during the adverse event reporting period should be reported as an adverse event and the appendectomy should be documented as the treatment method for the event.

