3.2 Inclusion Criteria

Inclusion criteria:

1. Age: ≥ 18 years old;
2. Patients strictly meeting the clinical diagnostic criteria in "Guideline on Diagnosis and Treatment for Primary Liver Cancer" (2011 Edition) or with histologically or cytologically confirmed recurrent/metastatic HCC, unsuitable for palliative surgery or radiation therapy, with at least one measurable lesion (must be ≥ 10 mm in longest diameter by spiral CT or ≥ 15 mm in shortest diameter for enlarged lymph nodes, as per RECIST 1.1, as shown in Annex 1);
3. Patients with HCC refractory or intolerant to systematic chemotherapy (with oxaliplatin, alone or in a therapeutic combination) and/or molecular targeted therapy with sorafenib;

Note: Definition of treatment failure: disease progression during treatment or relapse after treatment is completed (must have received ≥ 1 cycle of systemic chemotherapy with oxaliplatin (or plus other drugs) or ≥ 14 days of molecular targeted therapy with sorafenib);

Definition of intolerance: Grade $\geq IV$ hematological toxicity or Grade $\geq III$ non-hematological toxicity or Grade $\geq II$ major organ injury such as the heart, liver, or kidneys during treatment.

4. The interval between the last systemic treatment failure (with treatment discontinued) and the enrollment (time of signing the informed consent form) was ≥ 2 weeks, and the adverse event(s) had basically returned to normal (NCI-CTCAE \leq Grade I);
5. Child-Pugh score: Class A or Class B (≤ 7); the Child-Pugh scoring system is shown in Appendix 2;
6. BCLC staging: B-C (the "Barcelona Clinic Liver Cancer (BCLC) Staging System, 2010" is shown in Appendix 3);
7. ECOG PS of 0–1 within 1 week before enrollment, as shown in Appendix 4;
8. Expected survival ≥ 12 weeks;
9. HBV DNA < 2000 IU/mL (10^4 copies/mL);
10. Major organs must function normally, meeting the following criteria:
 - (1) Hematology: (without blood transfusion, G-CSF, or medication within 14 days prior to screening)
 - d. HB ≥ 90 g/L;
 - e. ANC $\geq 1.5 \times 10^9$ /L;
 - f. PLT $\geq 80 \times 10^9$ /L;
 - (2) Biochemistry: (no ALB transfusion within 14 days)
 - e. ALB ≥ 29 g/L;
 - f. ALT and AST $< 5 \times$ ULN;
 - g. TBIL $\leq 1.5 \times$ ULN;
 - h. Creatinine $\leq 1.5 \times$ ULN;
- (Only one of the two items, albumin or bilirubin, has a Child-Pugh score of 2)

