8.3.3 Management of gastrointestinal hemorrhage

Gastrointestinal hemorrhage, including fecal occult blood (++) and above, hematemesis or bloody stool, should be given active symptomatic treatment. Patients with upper gastrointestinal hemorrhage should be fasted and given acid suppression, gastric mucosal protection, hemostasis (transamin, reptilase, etc.), as well as octreotide if necessary; patients with lower gastrointestinal hemorrhage should be given hemostasis, blood transfusion and supportive care, etc.; for those whose bleeding cannot be controlled, assistance from the surgery department should be requested.

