### 4.1 Adverse Events

AEs, treatment-related adverse events (TRAEs), and SAEs that have occurred during the study period.

An AE refers to any untoward medical occurrence in a clinical investigation subject and which does not necessarily have a causal relationship with the treatment. AEs include but are not limited to: laboratory abnormalities; clinically significant symptoms and signs; allergies;

According to the needs of management, safety monitoring (reporting of AEs or SAEs) should be performed from the signing of the informed consent form by the subject to 28 days after the last dose.

Treatment-related AEs (TRAEs): All toxicities and unintentional reactions to a drug associated with any dose should be considered as Treatment-related AEs (TRAEs). Treatment-related AE means that a potential causal relationship between the drug and AE is at least reasonable, which means that the relationship cannot be excluded. The potential relationship between an AE and the investigational drug is assessed with 5 grades of causality: definitely related, probably related, possibly related, unlikely related, and not related. Events that are assessed to be "definitely related", "probably related", and "possibly related" are considered related to the investigational drug. When calculating the incidence of Treatment-related AEs, the total number of these three categories is used as the numerator and the total number of subjects in safety set is used as the denominator.

A SAE refers to a medical occurrence during the clinical trial that results in hospitalization, prolonged hospitalization, disability, incapacity, life threatening events or death, or congenital malformation. The following unexpected medical events are included:

- Events resulting in death;

- Life-threatening events (defined as events where the subject is at immediate risk of death at the time of the onset);
- Events resulting in hospitalization or prolonged hospitalization;
- Events resulting in permanent or serious disability/incapacity;
- Congenital anomalies or birth defects;
- Overdose;
- Pregnancy during the clinical trial.

Criteria for other SAEs specified in the protocol:

- Cardiac insufficiency — defined as any symptom or sign of reduced LVEF (NCI CTCAE Grade 3), or LVEF reduced by  $\geq 20\%$  from baseline and below the lower limit of normal (or reduced to  $< 50\%$ ).

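### Protocol 11.1.3 counts any admission caused by an adverse event as serious, then excludes an undefined class of emergency admissions, so an acute event can miss SAE reporting

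*Protocol*

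**What the plan says.** Protocol 11.1.3, under Hospitalization, first sets the rule: "AEs resulting in hospitalization or prolonged hospitalization should be considered serious AEs". It then makes the rule broad: "Any initial hospital admission by a medical facility meets this criterion (even if less than 24 hours").

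Two exclusion lists follow.

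- The first opens with "Hospitalization does not include the following". It names rehabilitation and sanatorium stays, day surgery, and "General emergency admission". The list carries no condition about adverse events, and the emergency term is not defined anywhere.
- The second opens with a condition: it concerns only admissions that have nothing to do with a worsening adverse event. Among its examples is "Hospitalization merely for use of blood products". The examples on pre-existing disease and on elective admission each restate the condition. The blood-products example does not.

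The section closes by saying that the condition behind a procedure is still to be reported if it is an adverse event. It does not say that it is to be reported as serious.

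SAP 4.1 repeats the SAE criteria, including "Events resulting in hospitalization or prolonged hospitalization", but contains neither exclusion list.

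**The concern.** Seriousness status does practical work in this protocol. It triggers the 24-hour report in 11.3 and notice to all sites in section 14. An SAE is also the named example of a signal for the safety committee in 11.5 and of a reason for unblinding in 11.4. A rule that lets two sites classify the same admission differently weakens each of these steps and makes the SAE table harder to read.

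The events most likely to be affected are ones the plan itself expects. The SAP lists hemorrhage as an adverse event of special interest, and Protocol 8.3.3 foresees transfusion as part of its management: "patients with lower gastrointestinal hemorrhage should be given hemostasis, blood transfusion and supportive care". An acute bleed may well arrive as an emergency admission, and an admission for anemia or low platelets may well be for transfusion. Those are the two kinds of admission that the exclusion bullets name.

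**Working it through.** No figure in the plan rests on these rules, so there is nothing to recompute. The check is to take typical cases through the general rule and through each list under its own lead-in.

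| Case (no other seriousness criterion met unless stated) | General rule | Exclusion lists | Result |
|---|---|---|---|
| Emergency admission for an acute GI bleed, under 24 hours | SAE | First list: not hospitalization | Direct conflict |
| Admission for transfusion because platelets have newly fallen | SAE | Second list read with its lead-in: not exempt. Bullet read alone: exempt | SAE, but easily misread |
| Planned admission for blood products, condition unchanged since baseline | No new or worse adverse event, so not an SAE | Second list: exempt | Consistent |
| Emergency-room visit, patient sent home | No admission | Not needed | Consistent |
| Fatal or life-threatening bleed | SAE on that criterion | Irrelevant | Consistent |

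**First row.** The second list's lead-in cannot resolve the conflict, because it does not govern the first list. A site that follows the general rule reports the case. A site that follows the first list does not.

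**Second row.** The lead-in settles the meaning. The risk is in use, because the bullet presents transfusion admissions as a typical non-event admission. In this population they often will not be. Entry requires Hb of at least 90 g/L and platelets of at least 80 × 10^9/L, "without blood transfusion, G-CSF, or medication within 14 days prior to screening", and albumin of at least 29 g/L without recent albumin infusion. A later need for blood products therefore often points to something new or worse.

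**What remains recorded.** All adverse events are graded and entered in the eCRF (Protocol 11.2). Hemorrhage also has its own term list in SAP Appendix 2. Anemia and platelet decrease are not among the events of special interest in SAP 7.4.1 or Appendix 2, so for them a wrong seriousness code has no such second route to attention.

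**Size.** The documents give no count of emergency or transfusion admissions. The nearest phase II figures do not supply one:

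- SAEs at 750 mg, 12/51 (23.5%), are events already classified as serious.
- Grade III–V platelet decrease at 750 mg, 7/51 (13.7%), says nothing about admission or transfusion.
- The four GI hemorrhages among early withdrawals were at 850 mg, a dose not used here. There were none at 750 mg, and withdrawals are not admissions.

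Any number of missed SAEs would need an assumed share of emergency admissions for which the documents give no basis.

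**The case against.** The strongest reply is that a broad rule followed by exceptions is ordinary drafting. The emergency bullet stands next to sanatorium stays and day surgery, which suggests that emergency-room attendance was meant. The text also appears to be a translation, so the word for admission may be an accident. This is a plausible account of the intention. It does not remove the problem, because the bullet speaks of admission, is undefined, and follows directly on a rule that counts even the shortest admission. A site has to apply the words it is given.

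On blood products the reply succeeds further. A reader might infer that the protocol exempts all admissions for transfusion and so contradicts its own general rule. It does not: the lead-in and the word for *merely* keep an admission for new bleeding or cytopenia inside the SAE definition. Nor does entry eligibility make every later transfusion a new event. The 14-day window does not rule out a long-standing deficit, and albumin between 29 and 35 g/L is allowed at entry and already scores 2 Child-Pugh points. Planned use for a stable condition is possible, and the bullet can properly cover it.

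On the SAP, a reader might infer a competing SAE definition. SAP 4.1 reads as a shortened restatement: it also leaves out the protocol's progressive-disease rule and the note on the bilirubin ratio, and nothing in it sets up a separate derivation of seriousness. A cross-reference is enough.

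**Conclusion.** The point holds for emergency admissions: two statements in Protocol 11.1.3 give opposite answers for the same case and must be reconciled. For blood products it holds only as an unclear example that needs its condition stated.

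The exposure is an event coded as non-serious and a missed 24-hour report, in cases that meet no other seriousness criterion. Its size cannot be estimated from the documents. Whether any case is missed depends on how sites read the emergency bullet, which the text leaves open.

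Two larger conclusions are tempting but unsupported. The first is that bleeding or cytopenia would disappear from the safety data; these events stay recorded as graded adverse events, and fatal or life-threatening ones are SAEs in any case. The second is that the SAE comparison would be biased in favor of apatinib. That would need more such admissions on apatinib than on placebo, which is a reasonable suspicion but is not shown: the phase II HCC trial compared two apatinib doses and had no placebo arm. The overall survival analysis is unaffected.

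**What to change.** In Protocol 11.1.3:

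1. Replace the emergency bullet with: *emergency-room visit that does not lead to admission*.
2. Replace the blood-products bullet with: *planned admission for blood products for a condition present and unchanged since baseline*.
3. Add one sentence: *admission for transfusion because of a new or worsening adverse event, such as bleeding, anemia or thrombocytopenia, is an SAE*.

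In SAP 4.1, refer to Protocol 11.1.3 for the hospitalization rules.

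If patients have already been treated under the present text, check admissions that were exempted under either bullet against the clarified rule before database lock.

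The cost is two bullets and one sentence in the protocol, one line in the SAP, and a few more SAE reports. No dose, treatment rule, endpoint or sample size changes.

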11.2 Recording and Evaluation of Adverse Events

All AEs should be described by terms in NCI-CTCAE 4.0 and recorded in eCRF accordingly. In addition, SAE Report Form (including initial or follow-up reports) should be completed. All subjects participating in the trial must be summarized. Reasons for withdrawal or rejection should be explained. A detailed individual report should be prepared if there is any death or serious toxic reaction in the trial. The cause of death, especially the relationship with the investigational drug, should be investigated. All AEs in the follow-up should be closely monitored until such events are properly resolved or the subject's condition is stable.

The following aspects of each AE should be recorded in the eCRF:

- (1) Onset time (start time) and recovery time (end time)
- (2) Assessment and classification of AE by investigator in accordance with NCI-CTCAE version 4.0. If the severity of several AEs is not classified in NCI-CTCAE, the investigator can evaluate the grade in accordance with NCI-CTCAE.
- (3) The potential relationship between the AE and the investigational drug can be assessed with 5 grades of causality: Definitely related, probably related, possibly related, unlikely related, and not related. Events that are assessed to be "definitely related", "probably related", and "possibly related" are considered related to the investigational drug. When calculating the incidence of adverse drug reactions, the total number of these three categories is used as the numerator and the total number of subjects in safety set is used as the denominator.

Table 12. Criteria for the causality between AEs and investigational drug

Criteria	Definitel y Related	Probably Related	Possibly Related	Unlikely Related	Not Related
Reasonable temporal relationship	Yes	Yes	Yes	Yes	No
Is the adverse reactions for this drug known?	Yes	Yes	Yes	No	No
Can the reasons for removal be improved?	Yes	Yes	Yes or No	Yes or No	No
Does the same event recur after re-challenging?	Yes	No	No	No	No
Can the event be explained by other reasons?	No	No	No	No	No

(4) Measures taken for the investigational drug (such as continued medication, dose reduction, continued medication after interruption, discontinuation, and other conditions, please explain in details).

(5) Outcome defined as follows: resolved, improved, not improved, and aggravated.

Note: If a patient experiences the same AE several times, it must be recorded and re-evaluated each time.

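### Causality Table 12 conflicts with the protocol's and SAP's own definition of a treatment-related event and cannot grade events that have another cause, so related-event counts may be inconsistent

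*Protocol*

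**What the plan says.** Protocol 11.2 says that the relationship between an adverse event and study drug can be assessed in five grades: Definitely, Probably, Possibly, Unlikely and Not related. The first three count as related. SAP 4.1 repeats this and says that "the total number of these three categories is used as the numerator", over the safety set.

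Table 12 gives the criteria in five rows:

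- Plausible timing: Yes in the first four grades, No for Not related.
- "Is the adverse reactions for this drug known": answered Yes for Definitely, Probably and Possibly, and No for Unlikely and Not related.
- Improvement on withdrawal of the drug (presumably; the printed wording is unclear): Yes for Definitely and Probably, either answer for Possibly and Unlikely, No for Not related.
- Recurrence on rechallenge: Yes for Definitely, No for the other four.
- "Can the event be explained by other reasons": answered No in every one of the five grades.

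Protocol 11.1.2 defines an adverse drug reaction by a causal relationship that is at least reasonable, "which means that the relationship cannot be excluded". SAP 4.1 uses the same standard for a treatment-related AE. Neither asks whether the reaction is already known. The SAP does not reproduce Table 12, and neither document says which text prevails if they disagree.

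**The concern.** Two rows of the only causality criteria in the protocol do not do their job.

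The last row is the same in every grade. An event plainly due to tumor progression or underlying liver disease has another explanation, so it fails every column, including Not related.

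The known-reaction row makes prior knowledge a condition of relatedness. A reaction not seen before cannot be Possibly related or higher, however convincing the timing and withdrawal evidence. The row also works in reverse: an event of a known type can never be Unlikely or Not related.

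Treatment-related AEs and SAEs are named safety endpoints (Protocol 2.3, SAP 4), and their incidence and severity are tabulated (SAP 7.4.1). Relatedness also bears on reporting: under Protocol 11.3, an SAE after the 28-day window is generally reported only if suspected to be drug-related. Sites that follow the table and sites that follow the definition could grade the same event differently.

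**Working it through.** The plan states no figure to reproduce. The check is whether the printed table can grade the events that it will meet.

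**Inputs.** The five rows of Table 12, in the order temporal, known, improves, recurs, other cause:

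| Grade | Temporal | Known | Improves | Recurs | Other cause |
|---|---|---|---|---|---|
| Definitely | Y | Y | Y | Y | N |
| Probably | Y | Y | Y | N | N |
| Possibly | Y | Y | Y or N | N | N |
| Unlikely | Y | N | Y or N | N | N |
| Not related | N | N | N | N | N |

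**Method.** Five yes/no answers give 2^5 = 32 patterns. Each is matched to every column that it satisfies.

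**Result for the table as printed.** Six patterns match a grade:

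- YYYYN: Definitely
- YYYNN: Probably and Possibly (an overlap that does not alter the related count)
- YYNNN: Possibly
- YNYNN and YNNNN: Unlikely
- NNNNN: Not related

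The other 32 − 6 = 26 match none.

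**Other cause = Yes.** Of the 16 such patterns, 0 match any grade.

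**Known = No.** Of 16 patterns, 0 reach a related grade, 2 are Unlikely, 1 is Not related and 13 match none. A not-known event that improves on withdrawal and recurs on rechallenge (YNYYN) has no grade, although that is strong evidence of causation.

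**Known = Yes.** Of 16 patterns, 3 reach a related grade, 0 reach Unlikely or Not related, and 13 match none. In the phase II HCC trial (Protocol 1.5.7, Table 6), bilirubin increase was reported in 62.9% and 47.1% of the two dose groups. Read literally, such an event could never be graded unrelated, even where liver disease explained it.

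**Against the definition.** Protocol 11.1.2 and SAP 4.1 would count YNYYN, YNYNN or YNNNN as related whenever the relationship cannot be excluded. Table 12 puts the first in no grade and the other two in Unlikely. That is a direct contradiction.

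**How common events judged unrelated may be.** Table 5 of Protocol 1.5.7 gives 13 + 12 = 25 of 121 subjects with an SAE and 3 + 3 = 6 with a serious drug reaction. If the second group is a subset of the first, 25 − 6 = 19 of 25 (76%) had no SAE judged related. Phase II may have used other criteria, so this is context and not an estimate of misgrading.

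**The case against.** The strongest reply is that the grade is a clinical judgement. Protocol 11.2 says that causality can be assessed in five grades. It gives no algorithm and does not say that Table 12 overrides 11.1.2. The SAP carries the broad definition and leaves the table out. Protocol 11.3 also expects investigators to judge some SAEs unrelated to study drug, so events with another cause were clearly meant to be gradable. The English is rough, and the last row may be a translation or typesetting slip. All of this stands, and it makes the effect conditional on how sites used the table.

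A reader might infer that related-event counts will be wrong. The documents do not support that. Counts are affected only where the table is applied as printed, and the all-No row, being identical in every column, does not itself move an event between related and unrelated.

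A reader might also infer that new safety signals are lost. That goes too far as well. All-cause AEs are tabulated by system organ class and preferred term and SAEs are listed (SAP 7.4.1), laboratory shift tables are produced (SAP 7.4.4), and SAEs up to 28 days after the last dose are reported whatever their cause. In a placebo-controlled trial, a new reaction can appear as an imbalance between arms without any causality grade.

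Nor is the error only towards under-counting. The known-reaction row can also keep known event types out of the unrelated grades, so the net direction is not determined.

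What the reply does not remove is the contradiction itself. Table 12 is titled as the criteria, nothing ranks it below 11.1.2, and a slip in a working table still has to be corrected.

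**Conclusion.** Table 12 disagrees with Protocol 11.1.2 and SAP 4.1, and its alternative-explanation row discriminates between no grades. As printed, 26 of 32 answer patterns have no grade, including all 16 with another cause, and no not-known reaction can enter the treatment-related numerator. These are counts of patterns, not of events, and they say nothing about how often each pattern occurs.

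If sites applied the table literally, treatment-related AE and SAE counts may be inconsistent between sites, with novel reactions under-counted and known reaction types not gradable as unrelated. The documents give no event counts by pattern, so the size of any miscount cannot be computed. All-cause AE and SAE summaries and the overall survival analysis do not depend on the table, and SAP 7.4.1 already treats P values for AE incidence as clinical reference only.

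The point rests on the table being printed as the sponsor intended. The row has all five entries and shows no sign of damage, but an error in translation cannot be ruled out. It should be corrected because it feeds a named safety endpoint at low cost; it does not threaten the primary conclusion.

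**What to change.** 1. **Last row.** Print Yes or No for Possibly related, and allow Yes for Unlikely and Not related. Leaving No for Possibly would exclude an event that either the drug or liver disease could explain, contrary to 11.1.2.
2. **Known-reaction row.** Print Yes or No in every column, so that prior knowledge informs the judgement but is a condition of no grade.
3. **Governing text.** State in Protocol 11.2 and SAP 4.1 that the cannot-be-excluded definition governs where the table disagrees. This is needed even after steps 1 and 2. Taking Yes or No for Unlikely and Not related in the last row, the matches are 2 patterns for Definitely, 8 for Possibly (which include Probably's 2 and coincide with Unlikely's 8) and 4 for Not related: 2 + 8 + 4 = 14 of 32. The table alone would therefore not separate Possibly from Unlikely and would still leave 18 patterns ungraded.
4. **Recorded grades.** Review causality grades already recorded, blind to treatment arm, before database lock, with attention to events graded Unlikely or Not related and to events with a competing cause.

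The cost is a table correction, a site notice and one sentence in the SAP, plus some re-assessment work, because a notice alone does not repair grades already entered. Causality is already collected, so no new data item is needed.
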